Please note that intra-operative testing is done to confirm that the device is properly connected, that the batteries effectively drive and control the device, and that the device contacts the proper therapeutic anatomical target. The stimulation parameters used to test the device and its relationship to each patient's anatomy in the operating room are not suitable as a guide for subsequent therapy. The nature of the anatomical relationship between the electrode(s) and the device is modified by the processes of wound granulation and healing so that the impedance characteristics and the exact anatomical relationship of the electrode to the target neurological tissue change during the post-operative period. As with other neuro-modulatory devices, the baroloop device is tested in the operating room, but the therapeutic stimulation delivered by the device is titrated only after ca. 2-3 weeks of healing has occurred. The intra-operative stimulation characteristics are not used to guide the titration to therapeutic effect - the device is tested in the operating room to make sure that it is operational, and the actual titration of stimulation to modify blood pressure will begin only after a period of post-surgical healing.

WARNING: Be aware of severe side effects, such as profound bradycardia.

If a severe side effect occurs (including severe bradycardia), stimulation must be stopped immediately, and appropriate corrective actions taken.

Any stimulation-related effects (blood pressure decrease, heart rate decrease, or any other possible response due to stimulation) should be recorded in the study Case Report Forms.

After intraoperative impedance, self-test and stimulation testing, set the IPG in shelf-mode by selecting 'Activate Shelf Mode' in the status dropdown menu on the Programmer screen.

WARNING: The IPG must be in INACTIVE MODE after implantation during the recovery from surgery.

4.23. 14-Day Follow-up Visit (+2 / -3 days)

- Clinical assessment of the subject;
- Physical examination;
- Changes of medication regimen;
- Review and assessment of adverse events;
- Office cuff blood pressure; and
- Initial testing and titration of stimulation to achieve up to a 20% reduction in systolic blood pressure or age-adjusted 2018 ESC/ESH treatment target office blood pressure (OBP), whichever blood pressure achieved during stimulation is lower.

N.B.:

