The purpose of titration is to determine which electrode(s) and which preset stimulation parameters (which deliver different levels of energy and strength of stimulation) provide an optimal blood pressure reduction at the lowest and most effect stimulation intensity. The preset collections of stimulation parameters were derived from animal studies and represent a limited range of the values tested in animals so that the minimally effective stimulation parameters determined during animal studies may be used in humans. The general strategy during the titration should be to select all individual active electrodes (inactive electrodes do not need to be tested) and deliver a low and a high intensity stimulation from among the preset stimulation sequences provided by the Sponsor to define the range of blood pressure responses possible in each patient. Thus, the presets may be used during the process of selecting an optimal dose

of baroloop stimulation, and the preset stimulation that provides an effect blood pressure reduction may be selected for therapeutic stimulation.

The immediate goal of each titration is to reduce the blood pressure slowly and modestly over a sequence of weeks. Therefore, the reduction in blood pressure should not exceed 20% of the blood pressure preceding the titration effort. Moreover, if the blood pressure at the time the patient returns for a titration visit is at or below the age-adjusted OBP target values described in the 2018 ESC/EHS Guidelines, then no additional titration need be done. If this is obtained during any one of the titration tests described above, the stimulation characteristics that achieved a blood pressure less than the age-adjusted OBP may be used as the therapeutic level of stimulation until the next follow-up visit so long as the titrated blood pressure is not lower than 80% of the baseline value just prior to the titration, and the patient has no symptoms of dizziness, orthostatic hypotension or other adverse effects.

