If a 20% reduction in baseline blood pressure is greater than the age-adjusted OBP target, then the target blood pressure should be approached in a series of incremental steps in which an intermediate target blood pressure not below 80% of the baseline blood pressure is targeted. This intermediate target blood pressure should then be maintained for a week (at least) until the next visit for further titration, when a further 20% reduction in blood pressure may be targeted so long as the patient has no symptoms of dizziness, orthostatic hypotension or other adverse effects

Once an effective set of stimulation parameters has been selected, this setting should be used for treatment until the next study visit, when the blood pressure response can be re-evaluated, and stimulation parameters may be adjusted as appropriate to reach the goal of a blood pressure less than the age-adjusted OBP target.

Once the first treatment stimulation level has been selected, the patient should be observed in the hospital for 24 hours (as noted above). The titration of blood pressure will be retested after 24 hours prior to discharge following the titration strategy described above over a more limited range of electrode combinations and preset stimulation values. If the treatment is well tolerated and no adverse effects of VNS are identified during the hospital stay, the patient may be discharged on the prescribed pattern of VNS. Patients need not be hospitalized following subsequent blood pressure/stimulation titrations so long as the patient has no symptoms of dizziness, orthostatic hypotension or other adverse effects.

It is the Sponsor's expectation that most patients will achieve an OBP less than the age-adjusted target of hypertension treatment within a small number of weekly titration sessions. If the titration process persists beyond 12 sessions (~ 3 months), it is permissible to extend the interval between titrations up to six weeks. The patient and physician may work together to achieve a titration schedule that achieves the age-adjusted target OBP as quickly as is safe.

N.B.: The IPG should be charged at every visit to the physician's office for follow-up. In the first four weeks of titration, the IPG will be recharged twice a week. After four weeks of titration, the IPG may be charged weekly when the well-being of the patient will also be assessed. There is no home charging possible in this First in Human Study.

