4.25. Follow-up titration every 7 days (\pm 2-3 days)

- Clinical assessment of the subject;
- Physical examination;
- Changes of medication regimen;

 neuroloop	Confidential	Protocol – The baroloop Study
--	---------------------	-------------------------------------

- Review and assessment of adverse events;
- Office cuff blood pressure; and
- Titration of vagal nerve stimulation should be repeated weekly to achieve up to a 20% reduction in systolic blood pressure or office BP < the age-adjusted 2018 ESC/ESH treatment target office blood pressure (OBP), whichever blood pressure achieved during stimulation is lower. The titration protocol described above should be followed each time the patient returns for adjustment of baroloop stimulation. The data from the IPG will also be downloaded at each visit for subsequent analysis.

4.26. 30-Day Follow-up Visit (+7 / -7 days)

- Clinical assessment of the subject;
- Physical examination;
- Changes of medication regimen;
- Review and assessment of adverse events;
- Office cuff blood pressure;
- Medication compliance testing;
- 24hr ABPM after observed therapy for hypertension;
- Quality of Life SF-36 questionnaire; and
- Further testing and titration of stimulation to achieve an OBP less than the age-adjusted target of hypertension treatment, as described in the titration directions.

4.27. 90-Day Follow-up Visit (+14 / -14 days)

- Clinical assessment of the subject;
- Physical examination;
- Changes of medication regimen;
- Review and assessment of adverse events;
- Office cuff blood pressure;
- Medication compliance testing;
- 24hr ABPM after observed therapy for hypertension;
- Quality of Life SF-36 questionnaire; and
- Further testing and titration of stimulation to achieve an OBP less than the age-adjusted target of hypertension treatment, as described in the titration directions

4.28. 180-Day Follow-up Visit (+14 / -14 days)

- Clinical assessment of the subject;
- Physical examination;
- Changes of medication regimen;

 neuroloop	Confidential	Protocol – The baroloop Study
--	---------------------	-------------------------------------

- Review and assessment of adverse events;
- Office cuff blood pressure;
- Medication compliance testing;
- 24hr ABPM after observed therapy for hypertension;
- Quality of Life SF-36 questionnaire; and
- Further testing and titration of stimulation to achieve an OBP less than the age-adjusted target of hypertension treatment, as described in the titration directions

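### Read literally, the titration bullets in 4.23 and 4.25 conflict with the 20% per-session cap in 4.24 when 80% of the starting systolic pressure is above target

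*Combined protocol and SAP*

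**What the plan says.** Section 4.23 (14-day visit, first titration) sets the goal as a systolic fall of up to 20% or the "age-adjusted 2018 ESC/ESH treatment target office blood pressure (OBP), whichever blood pressure achieved during stimulation is lower". Section 4.25 (weekly titration) repeats the rule with a small change: "or office BP < the age-adjusted 2018 ESC/ESH treatment target office blood pressure (OBP), whichever blood pressure achieved during stimulation is lower". Section 4.25 then adds: "The titration protocol described above should be followed each time the patient returns for adjustment of baroloop stimulation". Section 4.23 has no such sentence.

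Section 4.24 holds the titration instructions. It opens the dosing rule with "The immediate goal of each titration is to reduce the blood pressure slowly and modestly over a sequence of weeks" and continues that "the reduction in blood pressure should not exceed 20% of the blood pressure preceding the titration effort". A setting that takes pressure below target may be kept: "the stimulation characteristics that achieved a blood pressure less than the age-adjusted OBP may be used as the therapeutic level of stimulation", provided that "the titrated blood pressure is not lower than 80% of the baseline value just prior to the titration" and the patient has no symptoms. The high-pressure case has its own rule, which begins "If a 20% reduction in baseline blood pressure is greater than the age-adjusted OBP target". There the target is to be approached in stages, with an intermediate goal no lower than 80% of baseline, held for at least a week.

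The visit lists in 4.26 to 4.30 do not use the closing clause. They refer to the titration directions.

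**The concern.** The closing clause in 4.23 and 4.25 compares two blood pressures and picks the lower. For a patient whose pressure after a 20% fall would still be above target, the lower of the two is the target. The bullet then points past the 20% limit in the one situation where 4.24 says to stop at that limit and wait. No rule states which section takes precedence.

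The 20% cap is the numeric per-session limit in a first-in-human implant. Section 5.3 lists hypotension and syncope among the stimulation-related risks. A site that took its goal from the visit bullet could aim below the 4.24 floor, and 4.23 covers the first therapeutic exposure. Entry requires a systolic pressure of at least 140 mmHg and sets no maximum (4.6.1, item 2), so the affected pressures are admissible.

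**Working it through.** **Inputs.**
- Cap (4.24): at most a 20% fall per session, so the floor is (1 − 0.20) × S = 0.8 × S, where S is the pre-titration systolic pressure.
- Target T: sections 4.23 to 4.25 give no number. Section 2.2 gives 120–129 mmHg systolic for most patients, 130–139 for ages 65–80, and a general goal below 140/90. Eligible ages are 18 to under 80, so both age bands apply.
- The documents give no threshold in mmHg to reproduce. Their only figures for the limit are the 20% and 80% above.

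**Where the conflict starts.** The literal goal is min(0.8 × S, T). It exceeds the cap when T < 0.8 × S, that is, when S > T/0.8.

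| Target T (mmHg) | Reading of section 2.2 | T/0.8 (mmHg) |
|---|---|---|
| 120 | lower edge, most patients | 150 |
| 129 | upper edge, most patients | 161.25 |
| 130 | lower edge for 65–80, or below 130 for most patients | 162.5 |
| 139 | upper edge, 65–80 | 173.75 |
| 140 | below 140 | 175 |

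**Size of the literal goal.** Above the crossing point the fall asked for is (S − T)/S.

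| S | 4.24 floor | T = 129 | T = 130 | T = 139 | T = 140 |
|---|---|---|---|---|---|
| 170 | 136 | 24.1% | 23.5% | no conflict | no conflict |
| 180 | 144 | 28.3% | 27.8% | 22.8% | 22.2% |
| 200 | 160 | 35.5% | 35.0% | 30.5% | 30.0% |

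At S = 180 these goals lie 15, 14, 5 and 4 mmHg below the floor of 144. With the lower-edge target of 120 the fall would be (180 − 120)/180 = 33.3%.

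**Below the crossing point** the literal goal is 0.8 × S, exactly 20%, and the cap is not breached.

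**Cost of keeping the cap.** From S = 180, the first session stops at 144. The next needs (144 − 129)/144 = 10.4% or (144 − 139)/144 = 3.5%. Two sessions reach target from S up to T/0.64, which is 201.6 mmHg for 129 and 217.2 for 139, if each full 20% fall is achieved and held.

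**Separate, minor check.** Section 4.24 requires a second weekly visit for the first four weeks of titration. With a start at Day 14, or as late as Day 21, that runs to Day 14 + 28 = 42 or Day 21 + 28 = 49. The Table 3 footnote ends it at Day 30, which is 12 to 19 days earlier.

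**The case against.** The best defence is that the bullets do not contradict 4.24 at all. Both speak of a fall of up to 20%, which can be read as a ceiling. Section 4.24 is the dedicated titration section, covers each titration, states the limit three times and deals expressly with the high-pressure case. A site could hardly titrate from the bullet alone, because electrode selection, presets, stimulation timing and Finapres monitoring are set out in 4.24, alongside the cap.

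Most of this stands, and it lowers the likelihood of harm. Continuous recording, the 24-hour stay after the first titration and the no-symptoms condition lower it further. It does not remove the defect. On the ceiling reading, the closing clause can never select the target in this range, so the text agrees with 4.24 only if that clause is ignored. Section 4.25 carries both instructions in one bullet.

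Three stronger readings are tempting and not supported:
- **That the first titration has no cap because 4.23 lacks the cross-reference.** Section 4.24 applies to every titration and describes the first session, including the observation that follows it.
- **That patients would undergo falls of 28% or 35%.** These are arithmetic goals. No document shows that these presets produce such falls in humans, and section 2.5.5 says the efficacy of chronic stimulation in humans is unproven.
- **That the conflict starts at one fixed pressure.** The crossing point depends on which section 2.2 target a site uses.

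**Conclusion.** The point holds as a drafting conflict on a safety limit and should be fixed. The design itself, a 20% cap with a stepwise approach, is not in question. On the literal reading, the bullets ask for more than a 20% fall once the pre-titration systolic pressure exceeds target/0.8: about 161 to 163 mmHg for targets of 129 or 130, and about 174 to 175 for 139 or 140. Across all the section 2.2 readings the range is 150 to 175.

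This rests on the literal sense of the closing clause and on taking the systolic targets from section 2.2. Only systolic pressure was worked through, because the 20% limb of the bullets is systolic. The documents give no baseline pressure distribution, so the number affected among up to 10 subjects is unknown.

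**What to change.** In both bullets, delete the closing clause that picks the lower pressure and restate the rule along these lines: titration aims for office blood pressure, systolic and diastolic, below the age-adjusted target, but in no session may blood pressure be taken below 80% of its pre-titration value; if 80% of that value is still above target, stop there and approach the target in steps at least a week apart, as in 4.24. The wording should not be narrowed to systolic pressure, because the 4.25 goal is office pressure and the 4.24 cap is on blood pressure generally.

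Changing lower to higher would not be enough. At S = 150 and T = 139 the goal would become max(120, 139) = 139, while 4.24 aims below target and permits down to 120.

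Add to 4.23 the reference to the titration protocol that 4.25 already contains. Separately, change the Table 3 footnote so that the second weekly visit runs for the first four weeks of titration instead of ending at Day 30, and adjust the sentence after it to match.

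The cost is a short text correction and a note to sites, with Ethics Committee and Competent Authority approval under 10.3 if the change is classed as significant. No subjects are added, and no titration steps or visits beyond those that 4.24 already requires.

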4.24. Stimulation Settings/Titration First-in-Human

Blood pressure titration using VNS will take several 'titration sessions' to obtain optimal control of blood pressure. The titration sessions will take place weekly after the first titration is completed 14 days after surgery until the blood pressure has reached a target value less than the age-adjusted 2018 ESC/ESH treatment target office blood pressure (OBP). In between each titration session for the first four (4) weeks, the patient will return to the hospital or office where the titration takes place to have the IPG recharged, data downloaded from the IPG, and a check of OBP. Thus, there will be two alternating types of visits each week for the first 4 weeks of titration, one for titration, data downloading from the IPG and IPG charging and one for an OBP check, data downloading from the IPG and IPG charging.

After 4 weeks, titration may be done weekly, and the IPG charging may be done weekly when the titration is conducted. The titration process will continue until the target OBP is reached or the patient's responses to VNS are sufficiently reliable to allow less frequent follow-up after each new titration of OBP. Once a stable, target OBP is reached, blood pressure follow-up may occur at an interval appropriate for blood pressure control as determined by the treating physician.

During the first titration of baroloop stimulation, the Investigator should explore as fully as possible the range of responses to different electrode positions and stimulation settings so that an optimal set of stimulation settings may be selected with full knowledge of the range of responses in each subject at each visit.

During the titration of blood pressure responses to baroloop stimulation, each subject's blood pressure should be monitored continuously using a Finapres device. The patient should be supine and blood pressure and heart rate should be recorded continuously. After stable BP and HR are observed in the patient, the titration of the VNS may begin. Blood pressure responses to specific stimulation tests should be recorded by the Finapres device, and it is also important to record the baseline blood pressure and recovery periods after stimulation to characterize each patient's response to baroloop stimulation. The blood pressure should also

be measured using an arm cuff 60 seconds after the onset of the stimulation sequence. Each titration stimulation should last at least 2 minutes, and the arm cuff blood pressure should be measured 1 minute after the stimulation starts while the stimulation is still present, and once again 1 minute after the titration stimulation has stopped. These values establish the correlation between arm cuff blood pressure and Finapres readings, which will be useful for subsequent titration visits in each patient.

The Cuff completely surrounds the vagus, and some combinations of stimulation parameters can optimally increase the effective depth of penetration of the stimulating electric field into the vagus nerve. The IPG provides a biphasic charge-balanced stimulation to achieve cathodal activation of the vagus nerve, and the IPG has been programmed to provide specific combinations of the following stimulation parameters, so called presets, which may be selected using the Programmer:

- Amplitude in μ A
- Pulse width in μ s
- Repetition rate in Hz
- Duty cycles in ratios of ON-OFF-Sequences

Preset name	Amplitude (µA)	Pulse width (µs)	Frequency (Hz)	Duty cycle	Comment
Impedance	96	400	4 single pulses with distance of - 320µs	-	Used for impedance measurement
P1A	96	240	40	0.3	-
P1B	96	400	40	0.3	-
P1C	96	240	40	0.5	-
P1D	96	400	40	0.5	-
P2A	144	240	40	0.3	-
P2B	144	400	40	0.3	-
P2C	144	240	40	0.5	-
P2D	144	400	40	0.5	-
P3A	300	240	40	0.3	-
P3B	300	400	40	0.3	-
P3C	300	240	40	0.5	-
P3D	300	400	40	0.5	-
P4A	444	240	40	0.3	-
P4B	444	400	40	0.3	-
P4C	444	240	40	0.5	-
P4D	444	400	40	0.5	-
P5A	600	240	40	0.3	-
P5B	600	400	40	0.3	-
P5C	600	240	40	0.5	-
P5D	600	400	40	0.5	-
P6A	744	240	40	0.3	-
P6B	744	400	40	0.3	-
P6C	744	240	40	0.5	-
P6D	744	400	40	0.5	Used during Surgery Mode

The purpose of titration is to determine which electrode(s) and which preset stimulation parameters (which deliver different levels of energy and strength of stimulation) provide an optimal blood pressure reduction at the lowest and most effect stimulation intensity. The preset collections of stimulation parameters were derived from animal studies and represent a limited range of the values tested in animals so that the minimally effective stimulation parameters determined during animal studies may be used in humans. The general strategy during the titration should be to select all individual active electrodes (inactive electrodes do not need to be tested) and deliver a low and a high intensity stimulation from among the preset stimulation sequences provided by the Sponsor to define the range of blood pressure responses possible in each patient. Thus, the presets may be used during the process of selecting an optimal dose

of baroloop stimulation, and the preset stimulation that provides an effect blood pressure reduction may be selected for therapeutic stimulation.

The immediate goal of each titration is to reduce the blood pressure slowly and modestly over a sequence of weeks. Therefore, the reduction in blood pressure should not exceed 20% of the blood pressure preceding the titration effort. Moreover, if the blood pressure at the time the patient returns for a titration visit is at or below the age-adjusted OBP target values described in the 2018 ESC/EHS Guidelines, then no additional titration need be done. If this is obtained during any one of the titration tests described above, the stimulation characteristics that achieved a blood pressure less than the age-adjusted OBP may be used as the therapeutic level of stimulation until the next follow-up visit so long as the titrated blood pressure is not lower than 80% of the baseline value just prior to the titration, and the patient has no symptoms of dizziness, orthostatic hypotension or other adverse effects.

If a 20% reduction in baseline blood pressure is greater than the age-adjusted OBP target, then the target blood pressure should be approached in a series of incremental steps in which an intermediate target blood pressure not below 80% of the baseline blood pressure is targeted. This intermediate target blood pressure should then be maintained for a week (at least) until the next visit for further titration, when a further 20% reduction in blood pressure may be targeted so long as the patient has no symptoms of dizziness, orthostatic hypotension or other adverse effects

Once an effective set of stimulation parameters has been selected, this setting should be used for treatment until the next study visit, when the blood pressure response can be re-evaluated, and stimulation parameters may be adjusted as appropriate to reach the goal of a blood pressure less than the age-adjusted OBP target.

Once the first treatment stimulation level has been selected, the patient should be observed in the hospital for 24 hours (as noted above). The titration of blood pressure will be retested after 24 hours prior to discharge following the titration strategy described above over a more limited range of electrode combinations and preset stimulation values. If the treatment is well tolerated and no adverse effects of VNS are identified during the hospital stay, the patient may be discharged on the prescribed pattern of VNS. Patients need not be hospitalized following subsequent blood pressure/stimulation titrations so long as the patient has no symptoms of dizziness, orthostatic hypotension or other adverse effects.

It is the Sponsor's expectation that most patients will achieve an OBP less than the age-adjusted target of hypertension treatment within a small number of weekly titration sessions. If the titration process persists beyond 12 sessions (~ 3 months), it is permissible to extend the interval between titrations up to six weeks. The patient and physician may work together to achieve a titration schedule that achieves the age-adjusted target OBP as quickly as is safe.

N.B.: The IPG should be charged at every visit to the physician's office for follow-up. In the first four weeks of titration, the IPG will be recharged twice a week. After four weeks of titration, the IPG may be charged weekly when the well-being of the patient will also be assessed. There is no home charging possible in this First in Human Study.

